This will be a prospective, single arm pilot pharmacokinetic (PK) study. We will recruit 18 healthy, HIV-negative women aged 18 to 40 years who are using Nexplanon®/Implanon® for contraception and who are willing to take a reduced dose of EFV for 2 weeks. We will limit enrollment to women who have had the ENG implant in place 12 to 24 months to avoid the initial burst release of ENG after implant placement, and to target the time frame of concern based on case studies of contraceptive failures among women on HAART. Performing the study in women without HIV infection will allow us to evaluate any interactions between ENG and EFV without having to contend with the effects of other drugs that make up typical HAART regimens. A two-week course of EFV will be sufficient for EFV to reach steady-state concentration while minimizing exposure in these healthy volunteers. By using the reduced dose of EFV (400 mg daily instead of the standard 600 mg daily dose)

Over 6 weeks from study entry, we will perform twice-weekly (see visit schedule) quantitative assessments of serum ENG as well as serum hormone concentration analysis, pelvic ultrasound for markers of ovulation, and cervical mucus testing, as described below. Given the slow apparent clearance of ENG and based on previous PK studies, we estimate that sparse sampling will be adequate to assess changes in ENG clearance during EFV administration. EFV will be administered for 14 days from the beginning of the study, after collection of baseline samples for ENG concentration determination. All study procedures will take place at the Johns Hopkins Bayview Medical Center's Clinical Research Unit (CRU). All blood tests will be performed locally except for ENG concentrations, which will be performed at Columbia University

Date: January 5th, 2017

Principal Investigator: [name], MPH

Application Number: NA_00087585

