Secondary endpoints will be serum markers of ovulation (estradiol [E₂], progesterone [P], follicle stimulating hormone [FSH], and luteinizing hormone [LH]), as well as evidence of ovulation on cervical mucus exam and transvaginal ultrasound (presence and subsequent disappearance of a dominant follicle >15 mm diameter)[19]. Blood for hormone assays will be drawn at the Bayview CRU at the same time as samples for ENG and EFV. During these visits participants will also undergo a pelvic exam for cervical mucus assessment, and a pelvic ultrasound to look for ovarian follicular activity. Monitoring throughout the study will allow us to compare ovarian activity across time points through both ultrasound visualization and ovarian hormone testing (E₂ and P). Changes in cervical mucus quality secondary to the progestin activity of ENG provide secondary contraceptive effects that may be maintained even if ovulation occurs. Continued monitoring for several weeks after cessation of EFV will allow us to follow subjects for the equivalent of a normal menstrual cycle, to ascertain whether either contraceptive effect (ovulation suppression or cervical mucus quality) was altered. Urine pregnancy tests may be repeated throughout the duration of the study as needed.

Ultrasounds and venipuncture for LH, FSH, E₂ and P levels will occur in the CRU. A total of 20 mL of venous blood will be collected for each outpatient visit. FSH, LH, E₂, and P assays will be performed by the CRU at JHU. FSH and LH will be measured using the automated immunoradiometric assay (IRMA) system. Assay sensitivity of LH assays is 0.07 mIU/ml; assay sensitivity of FSH assays is 0.2 mIU/ml. P will be measured using an automated immulite chemiluminescent assay system. Assay sensitivity of the P assay is 0.05 ng/ml. E₂ will be measured via an ultra-sensitive competitive binding radioimmunoassay with sensitivity of 2.2 pg/ml. The EFV assay will be performed through the Johns Hopkins Hospital Clinical Pharmacology Analytical Lab, and will be measured via LC-MS/MS assay with a lower limit of quantification of 0.5 ng/ml.

An assay for ENG is not commercially available, but the Irving Institute for Clinical and Translational Research at the Columbia University Medical Center in New York has developed a validated assay. ENG concentrations will be measured by LC-MS/MS, and the assay has a lower limit of quantification of 50 pg/ml.

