Nexplanon®/Implanon® is the only contraceptive implant currently available in the United States, and is the most effective reversible contraceptive method with a failure rate of less than 0.05%[22]. As it is a progestin-only method, it is safe for use in women with a variety of medical comorbidities who are unable to take estrogen-containing methods. The World Health Organization Medical Eligibility Criteria (WHO MEC) rates Nexplanon®/Implanon® as category 1 (no restriction for use) for women with HIV/AIDS, and category 2 (advantages of use generally outweigh theoretical or proven risks) for women taking NNRTIs and PIs, due to theoretical concerns about decreased contraceptive efficacy related to drug interactions[23]. Case reports of 7 pregnancies occurring in 6 HIV-positive women taking efavirenz and Nexplanon®/Implanon® simultaneously suggest the concern about drug interactions between these two compounds may be more than theoretical[9-12]. Two recent clinical studies have demonstrated significant reductions in serum etonogestrel concentrations when women using Nexplanon® were treated for HIV infection using standard doses of efavirenz[13, 14]. Another study evaluating the concurrent use of a levonorgestrel contraceptive implant and either efavirenz- or nevirapine-based antiretroviral regimens for treatment of HIV found that women taking efavirenz experienced not only decreased levonorgestrel concentrations, but unplanned pregnancies as a result of contraceptive implant failures[15].

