- Serum hormonal markers of ovulation (P, E₂, LH, FSH)
- Presence of dominant follicle(s) on transvaginal ultrasound during and after EFV dosing
- Change in cervical mucus quality suggesting ovulation during and after EFV dosing

- c. Statistical plan including sample size justification and interim data analysis.

Sample size: We hypothesize that during co-administration of the ENG implant and reduced-dose EFV, we will detect a decrease in serum ENG concentrations, but that overall contraceptive effect will be maintained. We do not anticipate that any subjects will have a drop in ENG concentration below the threshold needed for ovulation suppression (90 pg/mL)[8]. Using a two-sided Wilcoxon test, a sample size of 15 will have 80% power (with an alpha of 0.05) to detect a 20% difference in ENG concentration between women taking EFV and historical controls. We plan to enroll 18 women to account for a potential 20% drop-out rate.

Data Analysis: We will calculate area under the curve (AUC) and maximum and minimum concentrations of each drug (C_{max} and C_{min}), as noted above. For hormone markers (LH, FSH, E₂, P) we will evaluate change over time as well as whether pertinent threshold levels are reached that could indicate that ovulation has occurred. All serum tests will be evaluated through the Johns Hopkins Division of Clinical Pharmacology, with the exception of etonogestrel concentrations as this assay is not widely available. Serum samples will be frozen and shipped to the Irving Institute for Clinical and Translational Research at Columbia University Medical Center in New York City, which will perform the etonogestrel assay.

Interpretation: If the pharmacokinetic parameters for etonogestrel that are seen in this interaction study are consistent with those published in the literature (less than 30% difference), we will conclude that there is no significant interaction between ENG and reduced-dose EFV. This would support the assertion that Nexplanon®/Implanon® is a safe and effective option for HIV-infected women taking reduced-dose EFV who desire long-acting reversible contraception. However, if two or more women out of a sample of 15 breach the threshold concentration needed for ovulation suppression, it will indicate a statistically and clinically significant decrease in ENG concentration and potential for decreased contraceptive efficacy.

Date: January 5th, 2017

Principal Investigator: [name], MPH

Application Number: NA_00087585

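### Section 7c lets ENG concentrations alone support a safe-and-effective statement that 14 days of EFV in about 15 women cannot carry

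*Combined protocol and SAP*

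**What the plan says.** All references are to the combined protocol and SAP.

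- **Favourable rule (Section 7c, Interpretation).** If the ENG parameters differ from published ones by less than 30%, the study will conclude that there is no significant interaction. The text continues: "This would support the assertion that Nexplanon®/Implanon® is a safe and effective option for HIV-infected women taking reduced-dose EFV".
- **Counter-rule (next sentence but one in effect, same paragraph).** If two or more of 15 women fall below the ENG level needed to suppress ovulation (90 pg/mL), this will count as a significant decrease with potential loss of efficacy.
- **Exposure (Section 4a).** "EFV will be administered for 14 days from the beginning of the study". Monitoring lasts six weeks. "Continued monitoring for several weeks after cessation of EFV" is meant to span the length of a menstrual cycle.
- **Pharmacodynamic data.** Section 2 makes pharmacodynamic change a secondary objective. Section 4a defines ovulation on ultrasound and a favourable mucus score. Section 7b lists hormones, follicles and mucus as secondary outcomes. The Data Analysis paragraph of 7c asks whether hormone levels suggesting ovulation are reached.
- **Primary outcome (Section 7a).** ENG before versus after two weeks of EFV.
- **Population (Section 5).** HIV-negative women with implants placed 12 to 24 months earlier, who agree to use a second contraceptive method.
- **Sample size (Section 7c).** "a sample size of 15 will have 80% power" "to detect a 20% difference in ENG concentration between women taking EFV and historical controls".
- **Stated scope (Section 9a).** Preliminary data to guide later efficacy studies in HIV-infected women.

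**The concern.** The favourable statement is about contraceptive safety and effectiveness in HIV-infected women, but the condition that triggers it is a comparison of drug concentrations. The study also measures whether women ovulate and whether cervical mucus becomes permissive, yet the Interpretation paragraph gives those results no part in the decision. A result of ENG within 30% of published values, at most one woman below 90 pg/mL, and one or more ovulations would still meet the written condition.

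The statement also reaches past the design in exposure (two weeks against continuing treatment), population (HIV-negative, one implant-age window) and precision (about 15 women). Section 3 describes implant failures in women on EFV, and Section 6 stresses avoiding unintended pregnancy on EFV. An overstated conclusion could therefore affect contraceptive advice.

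**Working it through.** **1. The plan's own figure.** N = 15 (two-sided Wilcoxon test, alpha 0.05, power 80%, 20% difference) cannot be reproduced because no SD or CV is given. Solving backwards, a one-sample or paired comparison needs a CV of about 0.25 (simulated signed-rank; 0.257 by noncentral t). A two-sample comparison of 15 with 15 needs about 0.18 to 0.19. Enrolment of 18 equals 15 × 1.2. What matters here is that N was set for a difference in concentration, not for a proportion of women ovulating or falling below a threshold.

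**2. What enters each rule.**

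| Result collected | Used in 30% rule | Used in two-of-15 rule |
|---|---|---|
| ENG concentration | yes | yes |
| LH, FSH, estradiol, progesterone | no | no |
| Ultrasound ovulation | no | no |
| Cervical mucus score | no | no |

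**3. Exposure.** 14/42 = 33% of study days are on EFV. After study entry, Table 1 schedules ultrasound and mucus assessment on 12 days (2, 7, 11, 14, 18, 21, 25, 28, 32, 35, 39, 42). Four of these, Days 2 to 14, fall within dosing. Table 1 has no EFV sample after Day 14. For 15 women, total follow-up is 15 × 6/52 = 1.7 woman-years, of which 15 × 2/52 = 0.6 is on EFV. Since a second contraceptive method is required, pregnancies could not measure implant effectiveness in any case.

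**4. Precision with no events.** With 0 events in n women, the exact (Clopper-Pearson) two-sided 95% upper limit is 1 − 0.025^(1/n).
- n = 15: 1 − 0.025^(1/15) = 0.218, or 21.8%. One-sided: 1 − 0.05^(1/15) = 0.181.
- n = 18, if all enrolled women complete: 1 − 0.025^(1/18) = 0.185.
- The counter-rule tolerates one woman below threshold. For 1 of 15 the exact interval is 0.2% to 31.9%.

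**5. Does the counter-rule protect the statement?** It fails to trigger with probability P(X ≤ 1) = (1 − p)^15 + 15p(1 − p)^14, where p is the true proportion of women who fall below threshold.
- p = 5%: 0.463 + 0.366 = 0.829
- p = 10%: 0.206 + 0.343 = 0.549
- p = 20%: 0.035 + 0.132 = 0.167

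It reaches 80% detection only when p is about 19%. It is a useful check, but weak at this size, and it is silent on ovulation.

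**The case against.** The strongest defence has four parts.

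**The favourable rule does not stand alone.** This is right. A reader who stops at the quoted sentence might infer that a mean within 30% settles the matter, but the counter-rule follows and is tied to ovulation suppression. It is nevertheless another concentration rule, so it does not close the gap.

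**Nothing says that ovulation results will be ignored.** Also right. A reader might infer that the plan discards them. The documents do not support that, because they are a secondary objective and are to be analysed. What stands is narrower: no written link runs from those results to the conclusion.

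**The wording is soft and the study is a pilot.** The sentence says support for an assertion, not proof of efficacy. It still goes further than Section 9a, which reserves efficacy for later studies.

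**The 14 days have a stated reason.** Section 4a cites EFV steady state and limiting volunteers' exposure. The documents do not show whether ENG would fall further with longer dosing, so a reader should not infer that the exposure is wrong. Nor does the plan claim that the four weeks off EFV demonstrate suppression on EFV. The point is only what may be concluded from the exposure chosen.

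It is also tempting to set 21.8% against the failure rate below 0.05% quoted in Section 6. That comparison should not be made. The first is a bound on the proportion of women ovulating or below a threshold, and the second is a pregnancy rate. Section 4a itself notes that mucus effects may persist despite ovulation. Excluding 0.05% with zero events would take ln 0.05 / ln 0.9995, about 5,990 women, which no pharmacokinetic study could meet.

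**Conclusion.** The point holds as a limit on the conclusion, not as a fault in data collection. Read as written, Section 7c allows a safe-and-effective statement from concentrations alone, and that statement could coexist with observed ovulation. With EFV on 33% of study days and an upper limit of 21.8% even for 0 of 15 events, the study cannot show contraceptive effectiveness under continued EFV. The documents do not support the stronger claims that the plan will disregard ovulation or that it declares efficacy proven.

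The interval assumes 15 evaluable women, each counted once as having or not having an event. It is 18.5% if all 18 complete. The detection probabilities assume independent women with a common probability. None of these figures depends on the unstated CV.

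**What to change.** Rewrite the Interpretation paragraph of Section 7c.

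1. **Limit the claim.** State the ENG change after 14 days of EFV in HIV-negative women in the implant-age window studied. State that contraceptive effectiveness under continued EFV was not assessed. Sections 4a and 5 give 12 to 24 months and the Abstract gives 6 to 30, so these need reconciling before the window is named.
2. **Name the comparator.** Say whether the 30% applies to each woman's own pre-EFV baseline, which matches the primary outcome in Section 7a, or to literature values.
3. **Add conditions.** Do not draw the favourable conclusion if the two-of-15 rule is met, or if any woman meets the protocol's ovulation definition at any visit during or after EFV. Covering both periods matters because an ovulation just after Day 14 should not pass unnoticed. Section 4a puts the follicle size both as above 15 mm and as at least 15 mm, so one form should be fixed.
4. **Report by period.** Give ovulation counts for Days 1–14 and Days 15–42 separately, each with an exact interval.

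No visit, sample or participant is added. The cost is a narrower permitted conclusion and an extra condition in the decision rule. That condition is strict: without a monitored run-in before EFV, an ovulation unrelated to EFV would also block the favourable conclusion.

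### Section 7c can support a safe-and-effective conclusion on PK alone, while its two-of-15 threshold rule has no stated error rate or power and is silent on zero or one breach

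*Combined protocol and SAP*

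**What the plan says.** Section 7c of the combined protocol and SAP makes three separate statements.

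- **Sample size.** For a two-sided Wilcoxon test against historical controls, "a sample size of 15 will have 80% power (with an alpha of 0.05) to detect a 20% difference in ENG concentration". No other power figure is printed. Enrolment is 18 women. The same paragraph hypothesises that contraceptive effect is maintained and puts the suppression threshold at 90 pg/mL: "We do not anticipate that any subjects will have a drop in ENG concentration below the threshold".
- **Interpretation, reassuring branch.** If ENG parameters differ from published values by less than 30%, the plan concludes that there is no significant interaction, and adds: "This would support the assertion that Nexplanon®/Implanon® is a safe and effective option for HIV-infected women taking reduced-dose EFV". The number of women below the threshold is not part of this condition.
- **Interpretation, adverse branch.** The rule applies "if two or more women out of a sample of 15 breach the threshold concentration needed for ovulation suppression", in which case "it will indicate a statistically and clinically significant decrease in ENG concentration and potential for decreased contraceptive efficacy". No null rate, target rate, error rate or power is attached to it.

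The plan does not say how zero breaches or exactly one breach is to be read, how the rule scales if the number of evaluable women is not 15, or whether a single low sample counts as a breach.

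**The concern.** The two branches of the Interpretation paragraph are not linked. With one breach and a PK difference under 30%, the adverse rule does not apply and the reassuring sentence is available as written, although the plan's own expectation of no breaches has failed. A reader who sees 80% power in the same section may also credit it to the breach rule, which it does not describe.

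The threshold is central to the study's purpose. Section 8a (Unintended Pregnancy) gives the goal as finding out whether reduced-dose EFV lowers ENG to a level at which ovulation might occur, and section 9a links falling below the threshold to earlier replacement of the implant. A reassuring conclusion should therefore show how much 15 women can say about the proportion who fall below 90 pg/mL.

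**Working it through.** **1. The plan's own figure.** The 80% cannot be reproduced, because section 7c gives no SD, CV, control mean or number of controls. It is attainable. For a one-sample or paired signed-rank test with n = 15 and two-sided alpha 0.05, simulated power for a 20% difference is 79.9% at a CV of 25% (standardised effect 0.20/0.25 = 0.80). For two samples of 15, a CV of about 18% is needed. So the figure is not shown to be wrong, but it concerns a difference in concentration and not a count of women below a threshold.

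**2. Inputs for the breach rule.** From section 7c: the rule fires at 2 or more, n = 15, with 18 enrolled. Assumptions: women are independent and share a breach probability p. The documents give no value of p, so a range is shown.

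**3. Chance that the rule fires.** P(X ≥ 2) = 1 − (1 − p)^n − n·p·(1 − p)^(n − 1).

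At p = 0.10 and n = 15: 0.90^15 = 0.206; 15 × 0.10 × 0.90^14 = 0.343; P = 1 − 0.206 − 0.343 = 0.451.

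| True rate p | P(0), n = 15 | P(1), n = 15 | P(≥ 2), n = 15 | P(≥ 2), n = 18 |
|---|---|---|---|---|
| 5% | 46.3% | 36.6% | 17.1% | 22.7% |
| 10% | 20.6% | 34.3% | 45.1% | 55.0% |
| 15% | 8.7% | 23.1% | 68.1% | 77.6% |
| 20% | 3.5% | 13.2% | 83.3% | 90.1% |

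Solving P(X ≥ 2) = 0.80 gives p = 18.7% for 15 women and 15.7% for 18. Solving for 0.50 gives 10.9% and 9.2%.

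**4. What zero or one breach leaves open.** Exact (Clopper-Pearson) two-sided 95% limits:

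- 0/15: upper limit 1 − 0.025^(1/15) = 21.8%.
- 1/15: lower limit 1 − 0.975^(1/15) = 0.2%. The upper limit solves (1 − p)^15 + 15p(1 − p)^14 = 0.025, giving 31.9%.
- If all 18 are counted: 0/18, up to 18.5%; 1/18, 0.1% to 27.3%.

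**5. Can a PK difference under 30% coexist with a breach?** Yes. A 25% fall takes any woman who starts below 90/0.75 = 120 pg/mL under 90 pg/mL. This is an illustration only, since the documents give no baseline ENG distribution. It shows that the 30% criterion, which concerns agreement with published values, does not by itself rule out individual breaches.

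**The case against.** The strongest reply is that the breach rule does not stand alone. A PK difference of 30% or more blocks the reassuring sentence whatever the breach count. Sections 2 and 4a also plan direct evidence on ovulation: repeated hormones, ultrasound with a definition of ovulation, and a scored mucus examination. Section 7c evaluates whether hormone levels that could indicate ovulation are reached. This stands, although none of these markers is written into the Interpretation criteria.

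It is tempting to read the 54.9% chance that the rule stays silent at p = 10% as a 55% chance of false reassurance. The documents do not support that. The plan never says that zero or one breach is reassuring in itself; it is silent. False reassurance also needs a PK difference under 30%, and both depend on the same fall in ENG. The joint probability cannot be computed without baseline levels and variability, so 54.9% is only an upper bound at that assumed rate.

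Nor can one say flatly that the rule misses more often than not. The 10% rate is an assumption, and under the same cut-off the majority reverses with 17 evaluable women (48.2% missed) or 18 (45.0% missed).

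Finally, this is a pilot, the wording is that the result would support an assertion, and powering only the main concentration comparison is ordinary practice. That is a fair reason not to ask for more women. It does not justify leaving the reassuring sentence without a statement of how little zero or one breach in 15 excludes.

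**Conclusion.** The point holds as a gap in the interpretation rules. As written, one breach can coexist with the safe-and-effective sentence, and the only rule tied to 90 pg/mL has no stated operating characteristics. On its own, that rule fires with probability 17% to 83% across true breach rates of 5% to 20% in 15 women, and reaches 80% only near 18.7%. Zero or one breach leaves rates of up to 21.8% or 31.9% inside the exact 95% interval.

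These results rest on independent women, a common breach rate and a defined breach. The last is missing: the plan does not say whether one low sample among the 13 sampling days is enough, and that choice changes the rate being tested.

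Two further inferences should not be drawn. The breach rule is not the plan's only safeguard, for the reasons given under the objection. The implant failure rate of under 0.05% in section 6 is also not a benchmark for it: that figure is contraceptive failure, whereas a breach is a serum concentration, and section 4a notes that mucus effects may persist even if ovulation occurs.

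**What to change.** Amend section 7c as follows.

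1. State that the 80% power applies to the Wilcoxon comparison and not to the breach rule. Print the rule's detection probabilities over a range of assumed rates.
2. Keep two or more breaches as the positive signal, but state that fewer than two is not by itself evidence that suppression is maintained.
3. Say what counts as a breach. Report the breach proportion among all women with at least one ENG sample on EFV, with an exact 95% confidence interval.
4. Require the safe-and-effective sentence to be accompanied and limited by that interval. Report any single breach explicitly as contrary to the plan's expectation of none.

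A rule that withholds the reassuring sentence unless there are zero breaches is not needed. It would be a debatable trade-off and would not close the gap, since 0/15 still leaves rates up to 21.8% open and occurs 20.6% of the time at a 10% true rate.

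The cost is wording and one interval, with no added women, visits or assays. The downside is that the conclusion becomes less favourable.
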